3.4 Research questions

On these premises, our research questions are:

- is it better to use higher RF powers for shorter times, than lower RF powers for longer times, to reduce the risk of oesophagus overheating and oesophageal temperature alerts?
- is the suggested LSI value of 5 on the LA posterior wall feasible or thwarted by frequent occurrence of temperature alerts leading to premature termination of RF delivery, regardless of maximum power?
- what is the impact of the different RF energy settings on PVI, acute pulmonary vein reconnection (PVR) and short-term clinical success of the AF procedure?
- which LSI value and RF power should be used during RF ablation on the LA posterior wall in order to achieve the best compromise between safety from oesophageal damage and lesion transmuralty and durability?

To these aims, the PiLOT-AF study aims to test different combinations of RF power and LSI during PV encirclement on LA posterior wall.

The rate of oesophageal alerts will be collected and compared for each procedure modality. The rate of first pass PVI and acute PVR (related to breakthrough signals on LA posterior wall), the procedure duration and RF ablation time will be also collected as clinical indicators of lesion transmuralty and acute procedure success. The freedom from AF at 6 months follow-up will be used as clinical indicators of lesion durability and short-term procedure success. The occurrence of any oesophageal symptoms at follow-up will be recorded as surrogate clinical indicators of oesophageal damage. All other procedural complications will be also recorded as safety outcomes.

No data are currently available on this topic. Therefore, this study has been designed as pilot study for power analysis and sample size calculation of a further main study.

This pilot study will hopefully give us some insights about the best combination of RF power, application time and target LSI to use during AF ablation on the LA posterior wall in order to achieve durable PVI with minimal risks of oesophageal damage.

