4. OBJECTIVES AND OUTCOME MEASURES

Objectives	Outcome Measures	Timepoint(s) of evaluation of this outcome measure (if applicable)

Primary Objective
 
To compare the risk of oesophageal damage associated with different RF settings during AF ablation on the LA posterior wall
	
Rate of oesophageal temperature alerts (defined as oesophageal temperature rise > 39°C) during RF ablation on the LA posterior wall
	
Index procedure

Secondary Objectives
 
1. To compare the acute success of the index AF ablation using different RF settings on the LA posterior wall
 
2. To compare the short-term success of the index AF ablation using different RF settings on the LA posterior wall
 
3. To compare the rate of oesophageal injury related to different RF settings on the LA posterior wall during the index AF ablation
	
1. Rate of first-pass PVI, rate of acute PVR related to breakthrough signals on the LA posterior wall, total procedure time and RF ablation time
 
2. Freedom from atrial fibrillation
 
3. Rate of oesophageal symptoms (difficult or painful swallowing, heartburn, acid reflux, sore throat, hoarseness, cough, nausea, vomiting, non-cardiac chest pain)
	
1. Index procedure
 
2. During the follow-up period (6 months)
 
3. During the follow-up period (6 months)

Tertiary objectives
 
To evaluate the rate of complications associated with the different RF settings
	
Pericardial effusion, TIA/stroke, phrenic nerve injury, pulmonary vein stenosis, open-heart surgery, death
	
Index procedure

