6. STUDY RISKS AND BENEFITS

6.1. Study risks

The patients taking part will be undergoing a standard AF ablation on the basis of clinical reasons (symptoms and no response to medical therapy). When compared with the ablation protocol currently used in our centre, the study ablation protocol differs only for the use of predefined RF powers and target LSI values during PV encirclement on LA posterior wall. All proposed values of RF power and LSI have been already tested and approved in preclinical and clinical studies. Therefore no additional risks are expected from the study procedure.

Standard risks associated with an AF ablation procedure in our centre:

- bruising in the groin, mild chest discomfort, a sore throat and palpitations, which are usually self-limiting, occur in 1 in 10-20 people
- femoral vascular injury requiring a minor surgical repair occurs in 1 in 200 people;
- cardiac perforation requiring a drain at the time of the operation occurs in 1 in 50-100 people;
- pulmonary vein stenosis requiring treatment is 1 in 500;
- TIA or stroke is approximately 1 in 200 people;
- needing urgent open-heart surgery is 1 in 500 people;
- fatal complication is estimated to be 1 in 1000 people;
- cancer secondary to fluoroscopy exposure during the AF ablation is negligible considering the average low radiation dose and the short fluoroscopy time used.

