8.2.2. Screening and Eligibility Assessment

It will include:

- a. demographics;
- b. exclusion of pregnancy or breast feeding in case of child-bearing age female;
- c. detailed collection of any relevant medical history, but especially concerning AF, heart (including left atrial size and left ventricular function on most recent echocardiogram if any) or oesophageal diseases;
- d. list of current medications and antiarrhythmic drugs previously taken;
- e. current heart rhythm on 12-lead ECG.

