8.4. Pre-discharge review

As part of standard care, each patient will be reviewed the day after the ablation procedure, before discharge. The current symptoms status and occurrence of any procedural complications will be investigated and an ECG will be performed to check the heart rhythm. As part of the research study, the patient will be advised to commence a symptom diary where to record occurrence of palpitations and/or any other cardiovascular symptoms as well as oesophageal symptoms (difficult or painful swallowing, heartburn, acid reflux, sore throat, hoarseness, cough, nausea, vomiting, non-cardiac chest pain).

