APPENDIX A: STUDY FLOW CHART

APPENDIX B: SCHEDULE OF TIMING OF STUDY APPOINTMENTS AND STUDY PROCEDURES

	Recruit-ment	Baseline visit	Study intervention	Pre-discharge review	Telephone f-up 1	Arrhythmia Clinic visit	Telephone f-up 2
Time since AF ablation	≥ 6 wks	- 1-2 wks	0	+ 1 d	+ 3 mts	3-4 mts	+ 6 mts
Study procedures							
Eligibility assessment	X	X					
Patient's information	X						
Informed consent		X					
Randomisation		X					
Demographics		X					
Medical history		X		X	X	X	X
ECG		X	X	X		X	
AF ablation			X				
Symptom diary instruction				X			
Symptom diary collection					X	X	X

d = day; f-up = follow-up; mts = months; wks = weeks.

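### Secondary outcome 3 takes any of nine common symptoms as oesophageal injury with no baseline record of them, so pre-existing symptoms count as injury and may dilute a difference between arms.

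*Combined protocol and SAP*

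**What the plan says.** Section 4 sets secondary objective 3 as a comparison of oesophageal injury between RF settings. Its one measure is "Rate of oesophageal symptoms (difficult or painful swallowing, heartburn, acid reflux, sore throat, hoarseness, cough, nausea, vomiting, non-cardiac chest pain"), assessed "During the follow-up period (6 months"). Section 3.4 says how the symptoms are to be read: "The occurrence of any oesophageal symptoms at follow-up will be recorded as surrogate clinical indicators of oesophageal damage". Neither section sets a condition on onset, worsening, severity, duration or attribution.

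Symptom recording begins after the procedure. At the pre-discharge review, the day after ablation, "the patient will be advised to commence a symptom diary" (section 8.4). In Appendix B the row "Symptom diary instruction" is marked only at that review, and diaries are collected at 3, 3-4 and 6 months.

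The baseline visit (section 8.2.2) includes "detailed collection of any relevant medical history, but especially concerning AF, heart", and the same item continues with "left atrial size and left ventricular function on most recent echocardiogram if any) or oesophageal diseases". Current medications are also listed. None of the nine symptoms is asked about. Section 7.3 excludes oesophageal conditions that rule out the temperature probe and has a general investigator-discretion clause, but it does not name reflux, heartburn or cough.

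Sections 11.2 and 11.3 plan chi-square tests between treatment groups for categorical outcomes and make no use of baseline data.

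**The concern.** All nine symptoms are common outside ablation. As the outcome is worded, a patient who had reflux or a cough for years and still has it during follow-up is an injury event. A patient with diagnosed reflux might be found from the history or the medication list. One with cough, hoarseness, nausea, sore throat or non-cardiac chest pain would generally not be.

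Three things follow:

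- Background symptoms of similar frequency in every arm shrink the visible difference between RF settings and add variance.
- The symptom rates come out too high. The study is meant to inform the sample size of a main study (sections 3.4 and 11.1), so inflated rates could be carried forward.
- With 20 patients per arm, background symptoms may be unevenly spread by chance. Without a baseline record nobody could see this.

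This is also the only listed outcome that captures clinical oesophageal harm, because the tertiary complication list contains no oesophageal event. Pre-procedure symptom status cannot be reliably reconstructed months later.

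**Working it through.** **The plan's own figure.** Section 11.1 wants 12 patients per group with primary outcome data and cites temperature alerts in 55-75% of ablations. An alert rate of 60%, inside that range, gives 12 / 0.60 = 20 per group and 4 x 20 = 80, the planned total. Section 8.2.3 also gives 20 per arm (four blocks of 20, five per arm in each). The size was set on temperature alerts, not symptoms, and this point does not alter it.

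**Inputs.** From the documents: four arms of 20 and a chi-square test. Assumed, because the documents are silent: a two-sided 5% level; injury-symptom rates i of 5% v 25%; and a share b of 10%, 20% or 30% with a pre-existing symptom that is still reported in follow-up, unrelated to arm or injury.

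**Dilution.** Observed rate = b + (1-b) x i, so observed difference = (1-b) x (i2 - i1).

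- b = 10%: 0.10 + 0.90 x 0.05 = 14.5%, and 0.10 + 0.90 x 0.25 = 32.5%; difference 18 points.
- b = 20%: 24% v 40%; difference 16 points.
- b = 30%: 33.5% v 47.5%; difference 14 points.

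The true difference is 20 points throughout. At b = 20%, a true 5% would be reported as 24%.

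**Power.** This is exact enumeration of the uncorrected chi-square test. New-onset counting keeps only patients symptom-free at baseline, so n falls to (1-b) x 20 = 18, 16, 14 per arm, or (1-b) x 40 = 36, 32, 28 per side.

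| b | 20 v 20, as planned | 20 v 20, new onset | 40 v 40, as planned | 40 v 40, new onset |
|---|---|---|---|---|
| 0 | 44% | 44% | 76% | 76% |
| 10% | 27% | 39% | 48% | 72% |
| 20% | 20% | 34% | 33% | 66% |
| 30% | 14% | 28% | 25% | 60% |

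The 40 v 40 columns pool two arms against two, a contrast the plan does not specify. For a four-arm chi-square with two arms at 5% and two at 25% (noncentral chi-square, 3 df), power as planned is 54%, 33%, 22% and 16% at b = 0, 10%, 20% and 30%.

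**Chance imbalance.** The SD of the difference in b between two arms of 20 is sqrt(2 x b x (1-b) / 20). This is 9 points at b = 10%, 13 at 20% and 14 at 30%. At b = 20% it is close to the 16-point difference the comparison would be looking for.

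**The case against.** The strongest reply is that randomisation balances pre-existing symptoms, patients are blinded to arm, and this is a secondary surrogate in a pilot too small to settle the question. Balance holds only in expectation, and equal background still shrinks the difference. The test allows for chance imbalance on average, but in this one trial it could produce an apparent difference that nobody could explain. The point on size stands: with 5% v 15% and no background at all, even a 40 v 40 contrast has only 35% power.

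It can also be said that baseline is not blank and that attribution is implied. Section 8.2.2 singles out oesophageal diseases and lists medications, and the synopsis speaks of symptoms of oesophageal injury. This stands in part. Diagnosed reflux may be identifiable, but the plan neither uses that information nor gives an attribution rule, and section 3.4 counts any symptom.

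A reader might infer more than the documents support:

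- *That a real difference will be masked.* This needs values for b and for the effect, and the documents give neither.
- *That a checklist would restore the power seen at b = 0.* It would not, since patients with baseline symptoms leave the new-onset count.
- *That section 6.1 supplies the background rate.* Its statement that "mild chest discomfort, a sore throat and palpitations, which are usually self-limiting, occur in 1 in 10-20 people" covers a group that also includes groin bruising, and it describes effects of the procedure. It is not a pre-ablation rate, and a baseline record would not remove these effects.
- *That a null symptom result will be read as safety.* The protocol plans no such conclusion.

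**Conclusion.** The gap is real. Followed as written, the plan counts pre-existing symptoms as oesophageal injury, and the information needed to separate them is not collected. The direction is certain for any non-zero b: rates are inflated and the expected difference is diluted by (1-b).

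The size depends on assumption. At 5% v 25% with b between 10% and 30%, pairwise power is 14-27% as planned and 28-39% with new-onset counting. Counting worsened symptoms as well was not modelled. The comparison stays low-powered either way, so the main gain is an interpretable symptom rate to carry into the main study. This is a worthwhile, inexpensive improvement to a secondary outcome and does not touch the primary outcome or the sample size.

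**What to change.** 1. At the existing baseline visit, record the same nine-item symptom checklist that the diary uses, and add it to section 8.2.2 and Appendix B.
2. In section 4, define secondary outcome 3 as any symptom that is new or worse than at baseline, and report it by arm together with baseline status.
3. Report symptoms present only at the day-1 review apart from those that persist or start after discharge. This is needed separately because a baseline record cannot remove effects of the procedure such as sore throat.

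The cost is one short checklist at a visit already planned, plus a protocol amendment. Patients already enrolled would lack the baseline record and would be reported under the present definition, separately from those who have it.

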1. SYNOPSIS

Study Title	Radiofrequency Power, Lesion Size Index and Oesophageal Temperature alerts during Atrial Fibrillation ablation: a pilot study	
Internal ref. no. / short title	PiLOT-AF study	
Study Design	Prospective, randomized, single centre observational clinical investigation	
Study Participants	Patients admitted for elective radiofrequency (RF) ablation for paroxysmal or persistent atrial fibrillation (AF)	
Planned Sample Size	80 patients (pilot study)	
Planned Follow-up duration	6 months	
Planned Study Period	15 months	
	Objectives	Outcome Measures
Primary	Assessment of the risk of oesophageal damage associated with radiofrequency (RF) ablation on the left atrial (LA) posterior wall when using different power settings	Luminal oesophageal temperature rises > 39°C during RF application on the LA posterior wall as recorded by an oesophageal temperature probe
Secondary	
Comparison of oesophageal complications with the different RF settings on LA posterior wall
 
Comparison of acute and short-term procedure success using different RF settings on LA posterior wall as marker of lesion transmural and durability
	
Symptoms of oesophageal injury during 6 months follow-up
 
Rate of first-pass pulmonary vein isolation (PVI), rate of acute pulmonary vein reconnection (PVR), total procedure time and RF time of the index ablation procedure
 
AF-free survival during 6 months follow-up

Tertiary	Comparison of rate of procedural complications using the different RF settings	pericardial effusion, TIA/stroke, phrenic nerve injury, pulmonary vein stenosis, open-heart surgery, death

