3.3 Oesophageal damage and atrio-oesophageal fistula after AF ablation

Unfortunately, deeper lesions mean a higher risk of overheating and damage of extra-cardiac structures close to the LA, in particular the oesophagus when ablating on the LA posterior wall. Heating of the connective tissue layer between the LA and oesophagus, containing oesophageal vascular structures, and of the oesophageal wall itself, are thought to contribute to the genesis of atrio-oesophageal fistulae, a rare but fatal complication of AF ablation (25).

In view of the variable position of the oesophagus relative to LA posterior wall, its positional changes over time and of the variable thickness of the posterior LA wall, fat pad and connective tissue layer between the LA and oesophagus, the prevention of oesophageal damage during AF ablation is quite challenging (26-29).

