8.5. Arrhythmia Clinic visit at 3-4 months

As part of standard care, each patient will be reviewed in the Arrhythmia Clinic 3-4 months after the ablation to assess the current symptoms status and check the heart rhythm on ECG. In the case of recurrence of AF, the decision to restart an antiarrhythmic drug and/or to plan a redo procedure will be left to the clinician involved in the care of the patient. Moreover, in accordance with usual practice, additional investigations as prolonged ECG monitoring will also take place dictated by arrhythmia symptoms and assessment for potential adverse events related to the procedure.

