10.2. Reporting Procedures for Serious Adverse Events

A serious adverse event (SAE) occurring to a participant should be reported to the REC that gave a favourable opinion of the study where in the opinion of the Chief Investigator the event was 'related' (resulted from administration of any of the research procedures) and 'unexpected' in relation to those procedures. Reports of related and unexpected SAEs should be submitted within 15 working days of the Chief Investigator becoming aware of the event, using the HRA report of serious adverse event form (see HRA website).

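### The tertiary complications outcome is timed at the index procedure only and does not name atrio-oesophageal fistula, so diagnosed late complications have no defined place in the comparison by arm.

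*Combined protocol and SAP*

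**What the plan says.** The tertiary objective in section 4 is "To evaluate the rate of complications associated with the different RF settings". The outcome is "Pericardial effusion, TIA/stroke, phrenic nerve injury, pulmonary vein stenosis, open-heart surgery, death", and the column for the time of evaluation reads "Index procedure". The synopsis repeats the six items ("pericardial effusion, TIA/stroke, phrenic nerve injury, pulmonary vein stenosis, open-heart surgery, death") without a time point. Fistula is in neither list.

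Other parts of the protocol bear on the same outcome:

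- Section 3.3 describes atrio-oesophageal fistula as "a rare but fatal complication of AF ablation".
- Section 3.4 says that all other procedural complications will be recorded as safety outcomes, with no window. It treats oesophageal symptoms at follow-up as surrogate indicators of damage.
- Section 4, secondary objective 3, compares oesophageal injury between settings through nine symptoms over the 6-month follow-up.
- Section 8.4, the day after ablation: "occurrence of any procedural complications will be investigated".
- Section 8.5 provides for further investigations under usual practice, prompted by arrhythmia symptoms and by "assessment for potential adverse events related to the procedure".
- Section 8.6 has calls at 3 and 6 months that collect symptoms and diary entries. Any further investigation is left to the clinical team.
- Section 10.2 limits reports to the ethics committee: "Reports of related and unexpected SAEs should be submitted within 15 working days".
- Appendix B has no row for complications or adverse events.

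**The concern.** The randomised power and LSI settings could cause harm that is diagnosed after the patient leaves the laboratory. If the complication rate by arm closes with the procedure, a later stroke, pulmonary vein stenosis or death has no defined place in it. A fistula or a confirmed oesophageal injury would enter the comparison only as a symptom, with the same weight as a sore throat. A patient who has died cannot report symptoms at a 3- or 6-month call.

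With 20 patients per arm, one uncounted event turns 1/20 into 0/20. The pilot is meant to inform a main study, and its safety table would then be incomplete in a way that readers could not see.

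**Working it through.** **1. What the time-point column means.** Within the section 4 table, temperature alerts, first-pass isolation, acute reconnection and procedure times carry the index-procedure label. Freedom from AF and oesophageal symptoms carry the 6-month follow-up label. The column therefore separates measures by when they are assessed, and complications sit in the first class. Section 8.4 (next day) and section 3.4 (no window) do not match that class, so the three places need reconciling.

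**2. Whether another route fills the gap.**

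- *Secondary objective 3* covers 6 months, but only oesophageal symptoms. It cannot capture a late stroke or pulmonary vein stenosis. It is also non-specific: section 6.1 puts a group of usually self-limiting effects, including sore throat and mild chest discomfort, at 1 in 10-20 people. Taken at face value that is 80/20 = 4 to 80/10 = 8 of 80 patients, and sore throat and non-cardiac chest pain are both on the symptom list.
- *Section 10.2* concerns reports to the ethics committee of related and unexpected events. It sets no comparison by arm, and a complication listed as a standard risk in section 6.1 could be judged expected.
- *Sections 8.5 and 8.6* generate clinical information, but no section returns a diagnosis to a defined outcome.

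**3. Size.** The plan makes no calculation for this outcome. Its one calculated figure, N = 80, reproduces as 4 × 12/0.60 = 4 × 20 = 80. The 60% alert rate is inferred, since section 11.1 gives only 55-75%; those ends give 4 × 22 = 88 and 4 × 16 = 64. The tertiary outcome plays no part in it.

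Expected events = 80 × risk, and chance of at least one = 1 − (1 − risk)^80, with risks from section 6.1:

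| Event | Risk | Expected in 80 | Chance of ≥1 |
|---|---|---|---|
| TIA/stroke | 1/200 | 0.40 | 33% |
| Pulmonary vein stenosis requiring treatment | 1/500 | 0.16 | 15% |
| Death | 1/1000 | 0.08 | 8% |

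Section 6.1 does not say when these events occur, so the figures are ceilings on late events at those risks, reached only if every event were late. Perforation is left out because section 6.1 describes it as drained during the operation, which the present time point already covers.

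The documents give no fistula rate. Over an assumed range:

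- 1/10,000: 80 × 0.0001 = 0.008 expected, 0.8% chance of at least one.
- 1/400: 80 × 0.0025 = 0.20 expected, 18% chance of at least one.

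**4. Precision.** The exact (Clopper-Pearson) two-sided 95% upper limit for 0/20 is 1 − 0.025^(1/20) = 16.8%. For 1/20 it is 24.9%. For 0/80 it is 1 − 0.025^(1/80) = 4.5%.

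**The case against.** The strongest reply is that later harm is not ignored. Secondary objective 3 compares oesophageal injury by arm for 6 months and ranks above the tertiary outcome. Section 3.4 promises to record all other procedural complications, without restriction to the six items. Sections 11.2 and 11.3 speak of comparisons and summaries at each time point, including follow-up visits. The index-procedure label could mean complications of that procedure, whenever found. A fatal fistula would be a death, which is listed. And with upper limits of 16.8% and 24.9%, no window would make the arms comparable on rare harms.

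Much of this stands, and it rules out some stronger readings:

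- A reader might infer that the trial leaves out later oesophageal harm altogether. It does not, because symptoms over 6 months are a formal secondary outcome.
- A reader might infer that the 3-4-month clinic is a scheduled complication review whose findings are discarded. Section 8.5 describes investigations under usual practice, not such a review.
- A reader might infer that late events will not be recorded at all. Section 3.4 does not support that.
- A reader might apply all the section 6.1 risks to the late period. That section gives no timing, and perforation belongs to the procedure itself.

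The reply does not settle the time point. The same table uses a follow-up label where follow-up is intended, and a promise to record is not a defined outcome with a window. Listing death does not help if deaths after the procedure fall outside the stated time.

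**Conclusion.** The point holds as one of definition and completeness. Read as written, the complication rate compared by arm stops at the index procedure, while sections 3.4 and 8.4 imply something wider. During follow-up, oesophageal harm is compared only through non-specific symptoms, fistula is not a named event, and other late complications are not a defined outcome.

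The size is modest. The three listed late-capable events with a stated risk sum to at most 0.40 + 0.16 + 0.08 = 0.64 expected events in 80 patients, with some possible overlap between stroke and death. Fistula adds 0.008 to 0.20 under the assumed rates. These figures assume that the centre's usual risks apply in all four arms.

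The primary outcome and N = 80 are unaffected, and the extra events would not support a test between arms. The change is still worth making: with counts this small, one missed event alters an arm's safety record, and correcting the wording costs little.

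**What to change.** - In section 4, change the tertiary time point to run from the index procedure to the 6-month telephone follow-up. Put the same window in the synopsis and section 3.4 so that they agree with section 8.4.
- Add to both complication lists: atrio-oesophageal fistula, or oesophageal injury confirmed on clinically indicated investigation.
- Add a complications row to Appendix B at the existing day-1 review, 3-month call, 3-4-month clinic visit and 6-month call.
- Record relatedness and date for each event.
- In section 11.3, state that counts will be tabulated by arm with exact 95% intervals, descriptively.

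The cost is protocol wording and, on the assumption that the case report form (not among the documents) lacks them, a few fields. No visit, test, extra patient or change to clinical care is involved. The drawback is that some unrelated late events will be counted; recording relatedness lets them be shown separately.
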